### **6.2. Handling of Dropouts or Missing Data**

With the exception of dates, missing data will not be imputed. The method of imputation for any dates that are imputed is described in the relevant section.

### **6.3. Patient Disposition**

A detailed description of patient disposition will be provided. It will include a summary of the number and percentage of patients enrolled in the study, randomized in the study, treated in the study, reasons for discontinuation from study treatment, and reasons for discontinuation from study. If the reason for discontinuation is adverse event (AE), the associated AE term will be reported. Patients who cross over from nivolumab to AM0010 in combination with nivolumab following progressive disease will be summarized as well.

Protocol violation will be summarized by treatment arm.

## **6.4. Patient Characteristics**

### **6.4.1. Demographics and Performance Status**

Patient demographics will be summarized. Patient demographics will include the following:

- sex
- race
- ethnicity
- age
- height
- weight
- body mass index

### **6.4.2. Baseline Disease characteristics**

Disease characteristics will be summarized. Variable of disease characteristics will include the following:

- time from initial diagnosis to randomization (months)
- initial diagnosis
- stage at initial diagnosis
- time from metastatic disease diagnosed date to randomization (months)
- PD-L1 tumor proportion score (%)
- tumor mutational burden
- smoking status
- baseline ECOG Performance Status

### **6.4.3. Medical History**

Medical history terms will be coded using the Medical dictionary for Regulatory Activities[MedDRA].

A summary for medical history will be presented including the count and percent of patients with any medical history record and also by body system and preferred term.

### **6.4.4. Prior Therapies**

Prior anti-cancer therapy and radiotherapy will be summarized. Line of prior anti-cancer therapy, prior anti-cancer therapy regimen, duration of the regimen, and the best response of the regimen will be summarized.

Prior radiotherapy, site, and duration of prior radiotherapy will be summarized.

Duration of the anti-cancer therapy and duration of the radiotherapy will be calculated as (therapy stop date – therapy start date + 1). If only month and year of a therapy is available, the day will be imputed using the 15th.

#### **6.4.5. Subsequent Anti-Cancer Therapies**

Therapies received following study treatment discontinuation will be summarized by treatment arm.

#### **6.4.6. Concomitant Medications**

All medications will be coded to the generic preferred name according to the current World Health Organization (WHO) drug dictionary. All concomitant medications will be summarized for the ITT population using the preferred name.

Selected concomitant medication such as steroid use will be summarized separately.

### **6.5. Efficacy Analyses**

#### **6.5.1. General Considerations**

##### **6.5.1.1. Population**

Unless otherwise noted, all efficacy analyses will be performed on the ITT population.

##### **6.5.1.2. Stratification Factors**

The stratification factor for the analysis of primary and secondary analyses are:

- histology type (squamous versus non-squamous)
- smoking history (current smoker, former smoker, and never smoker)

The stratification factors are captured in the IWRS and on electronic case report forms (eCRFs). Unless otherwise specified, all stratified analyses will be based on the stratification factor per IWRS. A cross tabulation of the frequency of each level of the stratification factor, histology type, per IWRS, and eCRF will be produced.

#### **6.5.2. Primary Endpoint: Objective Response Rate**

##### **6.5.2.1. Definition**

The primary efficacy measure is ORR as defined by RECIST version 1.1 and determined by the investigator.

The ORR is defined as the number of patients with a complete response (CR) or partial response (PR) divided by the number of randomized patients recorded between the date of randomization and the date of objectively documented progression or the date of subsequent anti-cancer therapy, whichever occurs first. For patients without documented progression or subsequent anti-cancer therapy, all available response designations will contribute to the ORR.

determination. For patients who continue treatment beyond progression due to suspected pseudoprogression is described in the protocol Section 7.6.

Rates and their corresponding 95% exact CI will be calculated by Clooper-Pearson method for each randomized treatment arm.

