| 
SAFETY ANALYSES
 | 
The primary efficacy endpoint is objective tumor response assessed according to RECIST v.1.1 criteria. Objective response rate and the corresponding 95% exact CI will be calculated by Clooper-Pearson method for each randomized arm.
 
Progression-free survival time will be summarized using Kaplan-Meier method to estimate the median PFS and 95% confidence interval (CI). Overall survival will be summarized in the same manner as the PFS.
 
Safety Population includes all randomized patients who received any amount of study drug. Trial treatment exposure will be summarized. Adverse events will be summarized in terms of treatment-emergent events, defined to be any event that begins or worsens in grade after first dose through 30 days after the last dose of trial drugs. Descriptive statistics of safety will be presented using NCI-CTCAE version 4.03 by treatment arm. All treatment-emergent AEs, treatment-related AEs, SAEs, treatment-related SAEs, and AEs leading to discontinuation from the trial treatments will be tabulated using worst grade per NCI-CTCAE v4.03 criteria by system organ class and preferred term. On-trial lab parameters including hematology and chemistry will be summarized using the worst grade per NCI-CTCAE v4.03 criteria.
 |
|-------------------------------|--|

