**Figure 1. Trial Design**

Trial sites will provide best supportive care per institution’s standard of care, including concomitant medications.

Arm 1 and 2 treatment will continue in the absence of disease progression, unacceptable toxicity, start of new anti-cancer treatment, or patient’s withdrawal of consent.

All radiological assessments will include, at minimum, scans of the head, chest, abdomen, and pelvis (CAPs).

At the time of documented disease progression (by Investigator assessment), patients in Arm 1 will be discontinued from the treatment period of the trial and continue on the follow-up period. At the time of documented disease progression (by Investigator

assessment), patients in Arm 2 may cross over to receive treatment with AM0010 and nivolumab.

Tumor assessment will be performed for all randomized patients every 8 weeks ( $\pm 7$  days) during the study treatment and during the first year from discontinuation of the study treatment, every 12 weeks ( $\pm 7$  days) during the second year, and every 16 weeks ( $\pm 7$  days) thereafter. Tumor assessment will be repeated until disease progression, death, or receipt of new anti-cancer therapy, or until study completion, whichever is first, whether or not study treatment was administered.

Confirmation of CR or PR is required. Confirmatory scans will be performed as follows:

- CR and PR criteria per RECIST v1.1 must be met again at least 4 weeks after initial documentation.

Patients with suspected pseudoprogression on scans in the absence of clinical deterioration should remain on trial treatments and be rescanned at 4 weeks or later as outlined in Section 7.6.

If progression is confirmed on follow-up scan, then discontinue treatments and follow trial procedures for end-of-treatment and survival follow-up or procedures for crossover patients.

Scans will include CAPs and head, and will be sent to the central imaging vendor for archiving and possible assessment at a later date. If clinical progression is suspected, all relevant clinical documentation is to be submitted to the central imaging vendor.

For patients who were randomized, but withdraw consent, survival (date of death) will be obtained by use of publicly available information.

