### **3.4 Trial Endpoints**

#### **3.4.1 Primary**

- The primary endpoint of this study is ORR, defined as the proportion of patients who achieve a CR or PR as assessed by RECIST v.1.1.

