### **10.2 Trial Endpoints**

#### **10.2.1 Primary Endpoint**

- **Objective Response Rate**

The ORR is defined as the proportion of patients with a confirmed CR or PR relative to the efficacy population. The ORR is determined by the best response designation per RECIST v1.1 recorded between the date of randomization and the date of objectively documented progression or the date of subsequent anti-cancer therapy, or death, whichever occurs first. For patient without documented progression or subsequent anti-cancer therapy, all available response designations will contribute to the ORR determination. Confirmed responses are those that persist on repeat imaging scan  $\geq 4$  weeks after initial documentation of response. For patients who continue treatment beyond progression due to suspected pseudoprogression as outlined in Section 7.6. The objective response should be determined based on response assessment recorded at the CT scan done no less than 4 weeks after suspected pseudoprogression. If the patient subsequently responds or returns to baseline, that assessment of objective tumor response is achieved after pseudoprogression as the true response per RECIST v.1.1.

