### **10.5.3 Efficacy Analyses**

#### **10.5.3.1 Primary Efficacy Analyses**

Objective response rate is defined as the proportion of patients who achieve confirmed CR+PR. Objective response rate and the corresponding 95% exact CI will be calculated by Clooper-Pearson method for each randomized arm.

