### **Antitumor Response (RECIST v1.1 Guidelines)**

Antitumor response will be defined as the percent of patients who achieve an objective confirmed response (complete or partial response). Disease control rate (SD for at least 16 weeks or confirmed CR or PR) also will be reported. Response will be determined according to RECIST guidelines. The original RECIST guidelines were developed and published in the Journal of the National Cancer Institute (Therasse, Arbuck et al. 2000).

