**Best Overall Response – Confirmation of CR and PR**

| Best Overall Response when Confirmation of CR and PR Required |  |   |
|---|--|---|
| Overall Response First Time Point                             | Overall Response Subsequent Time Point | Best Overall Response   |
| CR  | CR                                     | CR  |
| CR  | PR                                     | SD, PD or PR*   |
| CR  | SD                                     | SD provided minimum criteria for SD duration met, otherwise, PD |
| CR  | PD                                     | SD provided minimum criteria for SD duration met, otherwise, PD |
| CR  | NE                                     | SD provided minimum criteria for SD duration met, otherwise, NE |
| PR  | CR                                     | PR  |
| PR  | PR                                     | PR  |
| PR  | SD                                     | SD  |
| PR  | PD                                     | SD provided minimum criteria for SD duration met, otherwise, PD |
| PR  | NE                                     | SD provided minimum criteria for SD duration met, otherwise, NE |
| NE  | NE                                     | NE  |

Abbreviations: CR = complete response; NE = not evaluable; PD = progressive disease; PR = partial response; SD = stable disease.

\*If a CR is truly met at first time point, then any disease seen at a subsequent time point, even disease meeting PR criteria relative to baseline, makes the disease PD at that time point (since disease must have reappeared after CR). Best response would depend on whether minimum duration for SD was met. However, sometimes 'CR' may be claimed when subsequent scans suggest small lesions were likely still present and in fact the patient had PR, not CR at the first time point. Under these circumstances, the original CR should be changed to PR and the best response is PR.

Source: Eisenhauer, Therasse et al. 2009.

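### The SAP's primary ORR counts unconfirmed responses, while the protocol's primary ORR counts only confirmed ones

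*SAP*

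**What the plan says.** **SAP.** Section 6.5.2.1 defines the primary measure: "The ORR is defined as the number of patients with a complete response (CR) or partial response (PR) divided by" the number randomized, by investigator assessment under RECIST v1.1. It does not mention confirmation. Section 6.5.2.2 repeats the primary analysis on confirmed responses as ORR3. The revision history (SAP Section 3) describes this split as a clarification and calls the confirmed analysis an additional sensitivity analysis.

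**Protocol.**
- Section 3.0, after Figure 1: "Confirmation of CR or PR is required", with the criteria met again at least 4 weeks later.
- Section 10.2.1: "The ORR is defined as the proportion of patients with a confirmed CR or PR relative to the efficacy population", again with a repeat scan at least 4 weeks after the first.
- Section 10.5.3.1: "Objective response rate is defined as the proportion of patients who achieve confirmed CR+PR".
- Appendix D defines antitumor response as confirmed CR or PR. Its best-response table is titled "Best Overall Response when Confirmation of CR and PR Required".

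Two short protocol statements are silent on confirmation. Section 3.4.1 has ORR "defined as the proportion of patients who achieve a CR or PR as assessed by RECIST v.1.1". The synopsis says "The primary efficacy endpoint is objective tumor response assessed according to RECIST v.1.1 criteria".

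**Responses after suspected pseudoprogression.** Protocol 10.2.1 ends the response window at documented progression, then accepts a response seen after pseudoprogression as the true one. One of its sentences on this is unfinished. The corresponding SAP sentence is also unfinished and refers to Protocol 7.6, which defines further progression but gives no rule for counting responses. SAP 6.5.2.2 puts these responses in ORR4.

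**The concern.** A primary endpoint needs one numerator. Here the governing protocol sections and the SAP give different ones, and an analyst who follows the SAP will report a primary ORR that the protocol did not define.

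The label matters more than usual. SAP 6.1.1 makes all analyses descriptive by arm, so no test or threshold stands beside the estimate. Treatment is open-label, the investigator assesses response, and central review is only optional (Protocol 7.5). Confirmation is the protocol's own guard against a response called on one misread scan.

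The pseudoprogression wording adds a second ambiguity in the same numerator. Arm 2 patients may cross over at progression (Protocol 7.8.1). A response window that runs past progression without a stated limit could therefore credit the nivolumab arm with responses achieved on AM0010 plus nivolumab.

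**Working it through.** **1. Does RECIST v1.1 in the SAP already imply confirmation?** No. If it did, ORR3 would be identical to the primary analysis. The SAP lists the two separately, so its primary is the unconfirmed rate. The denominator is not in dispute: the SAP divides by randomized patients, and Protocol 10.4 makes the ITT population primary for efficacy.

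**2. The plan's own figures.** Inputs: n = 25 per arm, and 3, 6 or 8 responders (Protocol 10.3, SAP 5.2). The exact Clopper-Pearson limits are
- lower = the α/2 quantile of Beta(x, n − x + 1)
- upper = the 1 − α/2 quantile of Beta(x + 1, n − x)

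With α = 0.10:

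| Responders | ORR | Computed 90% CI | Stated |
|---|---|---|---|
| 3/25 | 12% | 3.4 to 28.2 | 3 to 28 |
| 6/25 | 24% | 11.0 to 42.0 | 11 to 42 |
| 8/25 | 32% | 17.0 to 50.4 | 17 to 50 |

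The stated intervals are reproduced.

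**3. What one unconfirmed responder does.** 1/25 = 4 percentage points. At the planned 95% level (α = 0.05):

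| Case | All CR/PR | One not confirmed | Two not confirmed |
|---|---|---|---|
| 8 responders | 32% (14.9 to 53.5) | 7/25 = 28% (12.1 to 49.4) | 6/25 = 24% (9.4 to 45.1) |
| 3 responders | 12% (2.5 to 31.2) | 2/25 = 8% (1.0 to 26.0) | not computed |

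The numbers not confirmed are assumed. Within an arm, confirmation can only lower the ORR or leave it unchanged.

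**4. Can responses be confirmed by the data cut?** SAP 6.8 sets the cut 6 months after the last randomization: 6 × 30.4375 = 182.6 days, or 26.1 weeks. Scans fall every 8 weeks, ±7 days.
- First response at week 16, latest case: 16 + 1 (window) + 4 (confirmation) + 3 days = 21.4 weeks, before the cut. The 3 days are the longest allowed gap from randomization to first dose, and adding them assumes that scans are timed from first dose.
- First response at week 24, earliest case: 24 − 1 + 4 = 27 weeks, after the cut.

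So only a patient randomized near the end of enrollment whose first response comes at week 24 is affected.

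**5. Secondary response endpoints side by side.**

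| Endpoint | No confirmation stated | Confirmation stated |
|---|---|---|
| DoR | Protocol 3.4.2, 10.2.2; SAP 6.5.3.4 | Protocol 10.5.3.2 |
| DCR | Protocol 3.4.2, SAP 6.5.3.3 (no SD minimum) | Protocol 10.2.2 (SD at least 9 weeks), Appendix D (SD at least 16 weeks) |
| Time to response | SAP 6.5.4.2 | Protocol 10.5.3.2 |
| Best response | SAP 6.5.4.1 | Appendix D table |

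The protocol glossary also exchanges the definitions of DCR and DoR. The Appendix D table needs an SD minimum to classify several unconfirmed CR/PR outcomes, so the conflicting SD durations affect it too.

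**The case against.** The strongest reply is that nothing is lost. ORR3 runs the same analysis on confirmed responses, no test or decision threshold depends on which rate is called primary, and both arms follow the same rule. A 4-point shift is small against a 95% interval about 39 points wide (53.5 − 14.9 = 38.6 at 8/25). Protocol 3.4.1 and the synopsis do not say confirmed, the SAP matches their wording, and its revision history records the choice openly.

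Part of this stands. The confirmed rate will be reported, the size is illustrative, and no bias between arms has been shown. But two short statements that are silent on confirmation do not override the explicit rules in Sections 3.0, 10.2.1, 10.5.3.1 and Appendix D. Calling the change a clarification does not acknowledge a departure from the protocol. With no formal test, the labelled estimate is the primary result.

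On pseudoprogression, it can be argued that Protocol 10.2.1 does count such responses, that its general confirmation rule covers them, and that the SAP excludes them by placing them in ORR4. On that reading the two documents simply disagree, which still calls for one rule. The crossover risk is also limited: patients with suspected pseudoprogression stay on assigned treatment until the rescan, a new baseline applies after crossover, and SAP 6.7.4 treats crossover patients separately. An explicit exclusion would close what remains.

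On DoR, the clock starts at first documentation in every version. Confirmation changes which patients are included, not the start date.

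**Conclusion.** The concern holds, with high confidence, and the primary-endpoint mismatch must be fixed. The SAP's primary ORR is unconfirmed, and the protocol's governing definitions require confirmation. Each unconfirmed responder is worth 4 percentage points in an arm of 25. How many there would be cannot be known from the documents, so the worked cases are examples and not forecasts.

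The pseudoprogression rule needs clarifying, and its effect cannot be sized from the documents. The secondary-endpoint differences are conforming edits and would not carry this rating alone.

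**What to change.** 1. **Primary ORR.** In SAP 6.5.2.1, make confirmed CR/PR, with the repeat scan at least 4 weeks later, the primary. Move the unconfirmed rate to the ORR3 position as the sensitivity analysis. Add the word confirmed to Protocol 3.4.1 and the synopsis. Amending the protocol to the unconfirmed rate, with a stated rationale, would also end the contradiction, but it gives up the check on single-scan calls.
2. **Pseudoprogression.** Put one rule in both Protocol 10.2.1 and SAP 6.5.2.1: whether a response after suspected pseudoprogression counts in the primary ORR, and whether it needs a further confirming scan. Report the other choice as ORR4. If such responses count, exclude those after the first crossover dose in Arm 2.
3. **Secondary endpoints.** Put DoR, time to response, best response and DCR on the same basis as the primary, with one SD minimum. This touches Protocol 3.4.2, 10.2.2 and Appendix D, and SAP 6.5.3.3, 6.5.3.4, 6.5.4.1 and 6.5.4.2. Correct the two glossary entries.

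**Cost.** Item 1 is a wording swap in the SAP plus one word in two protocol places. Items 2 and 3 are wording edits in several sections of both documents, so a protocol amendment or clarification is needed. Sample size, CI method and scan schedule do not change. The ORR may come out slightly lower, and a late first response may miss confirmation by the cut. The unconfirmed sensitivity analysis would still show such a patient.

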### **7.5 Tumor Assessments**

- CT or MRI (if allergic to contrast media) scans will be performed every 8 weeks ( $\pm 7$  days) during the study treatment and during the first year from discontinuation of the study treatment, every 12 weeks ( $\pm 7$  days) during the second year, and every 16 weeks ( $\pm 7$  days) thereafter, to evaluate response to treatment by RECIST v.1.1.
- The same radiographic procedure (includes head and CAPs) to define measurable lesions must be used throughout the trial for each patient.
- Patients will continue the assigned trial treatments until tumor progression (by RECIST v.1.1 criteria) by CT or MRI (if allergic to contrast media), withdrawal from the trial, or intolerance of therapy not manageable with dose modifications outlined in the protocol/package insert and/or supportive care. Note: patients with suspected radiographic pseudoprogression, in the absence of clinical deterioration, should remain on trial treatments and be rescanned at 4 weeks or later. If progression is confirmed on follow-up scan, study treatments will be discontinued or patients on Arm 2 may be eligible for crossover. Refer to Section 7.6.
- Patients who discontinue trial treatments with response of CR, PR, or SD will undergo CT or MRI scan evaluations per protocol until time of PD, death, study completion, or initiation of subsequent anti-cancer therapy, whichever is first.
- Patients who demonstrate clinical progression before their scans are due will have an unscheduled scan conducted to document disease status by RECIST v.1.1.
- The first scheduled tumor response assessment will be performed at 8 weeks ( $\pm 7$  days), and responders (CR or PR per RECIST v1.1) will have a confirmatory scan at  $\geq 4$  weeks after response has been established using the same technique as baseline scans.
- All CT/MRI scans for all patients randomized on the trial will be collected prospectively and submitted to a central imaging vendor for archiving. These scans may be independently reviewed at a later time at the request of Lilly.

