## **7.8 Continued Treatment**

### **7.8.1 Crossover**

At the time of disease progression (as assessed by the Investigator) patients randomized to trial Arm 2 may crossover to study Arm 1 to receive AM0010 and nivolumab. When progressive disease is noted on the scan for an ARM 2 patient, no more than 21 days should pass before the patient crosses over to ARM 1. The scans and/or clinical assessment at crossover will be used as a new baseline to determine response or PD on ARM 1.

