### **6.1.2. Definitions and Conventions**

Study treatment refers to AM0010 + nivolumab or nivolumab.

The date of randomization is the date the patient was randomly assigned to AM0010 + nivolumab arm or nivolumab arm using the IWRS.

The date of **first** dose is the date of the first dose of any study treatments.

The baseline value of a safety assessment is the last value observed prior to the date of first dose.

The study day of a safety event or assessment will be calculated as:

- The difference between the date of the event or assessment and the date of first study dose plus 1 for all events or assessments occurring on or after the day of first dose. For example, if an event occurs on 08 June 2018 and the date of first dose was 06 June 2018, the study day of the event is 3.
- The difference between the date of the event or assessment and the date of first dose for all events or assessments occurring before the day of first dose. For example, if an event occurs on 05 June 2018 and the date of first dose was 06 June 2018, the study day of the event is -1.

The study day of an efficacy event or assessment will be calculated as:

- the difference between the date of the event or assessment and the date of randomization plus 1 for all events or assessments occurring on or after the date of randomization.
- the difference between the date of the event or assessment and the date of randomization for all events or assessments occurring before the date of randomization.
- 1 month = 30.4375 days
- 1 year = 365.25 days

Unless otherwise noted, summaries of continuous variables will include a mean, median, standard deviation (SD), minimum, and maximum.

Unless otherwise noted, summaries of categorical variables will include the frequency and percentage (relative to the population being analyzed) of each category.

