### **6.5.4. Other Efficacy Analyses**

#### **6.5.4.1. Best Objective Response Rate**

Best objective response is calculated based on the overall visit response from each tumor assessment. It is the best response a patient has had following randomization but prior to starting any subsequent cancer therapy, prior to documented progression (clinical progression or

progression per scan) or the last tumor assessment in the absence of documented progression and subsequent cancer therapy.

Best objective response will be summarized using the following response categories: CR, PR, SD, progressive disease, and not evaluable.

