#### **6.5.4.3. Change in Tumor Burden**

Percentage change from baseline in tumor burden will be calculated at each tumor assessment. Best percentage change from baseline in tumor burden will be calculated as the biggest decrease or the smallest increase in tumor burden from baseline.

Tumor burden is defined as the sum of the longest diameters of the target lesions (the measurable tumor lesions).

The percentage change from baseline in tumor burden is calculated as:

- $(\text{Sum of target lesions at week } x - \text{sum of target lesions at baseline}) / \text{sum of target lesions at baseline} * 100$

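### ORR, best objective response and tumor change do not share one stated evaluation window in the SAP, so a CR or PR first seen after clinical progression counts in ORR but not in the best-response table

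*SAP*

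**What the plan says.** **Primary ORR (SAP 6.5.2.1).** Responses count from randomization until "the date of objectively documented progression or the date of subsequent anti-cancer therapy, whichever occurs first". Clinical progression is not named. The next sentence drops the word 'objectively', and SAP 6.5.3.1.1 uses 'documented progression' to include clinical progression, so the section is not quite consistent within itself.

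**Best objective response (SAP 6.5.4.1).** Only what is seen "prior to starting any subsequent cancer therapy, prior to documented progression (clinical progression or" counts; the bracket goes on to add progression on a scan. "Best objective response will be summarized using the following response categories: CR, PR, SD, progressive disease, and not evaluable", so the table yields its own CR+PR count.

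**Duration of response (SAP 6.5.3.4).** It runs from the first CR or PR to the first progression, clinical or by scan, or death.

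**Change in tumor burden (SAP 6.5.4.3).** The change is computed at every tumor assessment, and the section then reduces that series to one value per patient: "Best percentage change from baseline in tumor burden will be calculated as the biggest decrease or the smallest increase in tumor burden from baseline". No event closes the period.

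**Scans after progression (Protocol).** Section 7.5: "Patients who demonstrate clinical progression before their scans are due will have an unscheduled scan conducted to document disease status by RECIST v.1.1". Section 7.6 allows treatment, with a rescan, beyond a first RECIST progression. Section 7.8.1 lets Arm 2 patients cross over at investigator-assessed progression: "The scans and/or clinical assessment at crossover will be used as a new baseline to determine response or PD on ARM 1".

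**The intended link (Protocol 10.2.1).** ORR is derived from the best response designation, within a single window that ends at objectively documented progression, subsequent therapy or death.

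**The concern.** Under Protocol 10.2.1, ORR is the CR+PR share of the best-response distribution, so the two should agree by construction. In the SAP they need not. The best-response window lies inside the ORR window, and the scan called for after clinical progression falls in the gap. One scan is enough to make a responder there, because the SAP's primary ORR does not require confirmation (confirmed response is the additional analysis ORR3 in 6.5.2.2).

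At stake are two responder counts from the same scans and a secondary endpoint with an impossible value for the discordant patient. In addition, a tumor-change summary could include shrinkage reached after progression. In Arm 2 this could include shrinkage reached on the combination, which would blur the contrast between arms in an open-label trial with descriptive analyses.

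**Working it through.** **1. The plan's own figures.** Inputs: n = 25 per arm; 3, 6 or 8 responders (SAP 5.2). Exact (Clopper-Pearson) limits are

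- lower = Beta⁻¹(α/2; x, n − x + 1)
- upper = Beta⁻¹(1 − α/2; x + 1, n − x)

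At 90%: 3/25 gives 3.4 to 28.2%, 6/25 gives 11.0 to 42.0%, and 8/25 gives 17.0 to 50.4%. All agree with the stated intervals after rounding.

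**2. The windows side by side.**

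| Summary | Clinical progression closes it? | Scan progression closes it? | New therapy closes it? | Crossover named? |
|---|---|---|---|---|
| ORR, 6.5.2.1 | No | Yes | Yes | No |
| Best response, 6.5.4.1 | Yes | Yes | Yes | No |
| Best tumor change, 6.5.4.3 | Not stated | Not stated | Not stated | No |

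The best-response window can never outlast the ORR window, so the ORR count is at least the CR+PR count in the table.

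**3. One patient traced through (assumed dates).** Clinical progression on day 50; the resulting scan on day 54 shows PR; no earlier post-baseline scan.

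- ORR: responder, since neither closing event has occurred.
- Best response: not PR, since no scan precedes progression.
- PFS (Table JZGD.6.1, clinical progression rule): event on day 50.
- Duration of response: starts day 54, ends day 50; 50 − 54 = −4 days. The fallback to the PFS censoring time does not help, because this patient's PFS is an event.

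**4. Size per discordant patient.** 1/25 = 4.0 percentage points. With 95% exact intervals:

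| Responders | Without the patient | With the patient |
|---|---|---|
| 3 vs 4 | 12% (2.5 to 31.2) | 16% (4.5 to 36.1) |
| 6 vs 7 | 24% (9.4 to 45.1) | 28% (12.1 to 49.4) |
| 8 vs 9 | 32% (14.9 to 53.5) | 36% (18.0 to 57.5) |

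The documents do not allow the number of such patients to be derived. Assuming 0 to 1 per arm, the gap is 0 to 4 points.

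**5. Tumor change with and without a cut (assumed sums).** Baseline 100 mm; week 8, 125 mm (scan progression); week 12, 60 mm on treatment beyond progression.

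- Cut at progression: (125 − 100)/100 = +25%.
- No cut: (60 − 100)/100 = −40%.

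**6. Crossover.** The SAP excludes this period explicitly for cumulative dose (Table JZGD.6.2) and control-arm adverse events (6.7.4), and censors at it in the OS sensitivity analysis (6.5.5.2). Sections 6.5.2.1 and 6.5.4.3 have no such exclusion. SAP 6.1.2 states "Study treatment refers to AM0010 + nivolumab or nivolumab", so it is not settled that crossover counts as subsequent anti-cancer therapy.

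**The case against.** **The tumor-change section is silent; it does not instruct.** A reader might infer that post-progression scans will enter the results. The SAP does not say so. Scheduled scans normally stop at progression or new therapy (Protocol 7.1), which leaves mainly treatment beyond progression and crossover. This stands: later scans *can* enter, and no more can be said.

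**Crossover is handled elsewhere.** SAP 6.7.4 analyses crossover patients separately and takes the last assessment before crossover as their new baseline, which suggests that those scans do not belong in 6.5.4.3. For ORR, a crossover after scan progression is already outside the window; only crossover on clinical grounds stays open. Reading 6.1.2 as keeping such scans in ORR is an inference, since that section does not discuss crossover. This narrows the point, but neither efficacy section states the exclusion.

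**The size for Arm 2 is unknown.** It is tempting to put a percentage on how much of the Arm 2 tumor-change summary would reflect AM0010. The documents give neither a crossover fraction nor a shrinkage rate. Post-crossover shrinkage also matters only if it beats the patient's earlier best against the study baseline. No such figure is supported.

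**The primary measure is clear.** A reader might infer that one cannot tell which figure answers the primary objective. SAP 6.5.2.1 names ORR as the primary efficacy measure, and the other two summaries sit under 'Other Efficacy Analyses'. That inference fails.

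**The traced patient is unusual.** A PR days after clinical progression should be rare, and Protocol 7.6 lets some deterioration be recorded as symptomatic deterioration instead. This limits the frequency but leaves the mismatch in the definitions.

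**Conclusion.** The inconsistency is real but likely to be small. ORR closes at objective progression; best objective response and duration of response close at clinical or scan progression. The trial calls for scans that can fall between the two. Each discordant patient is worth 4 points in an arm of 25, and gets a duration of response that ends before it begins. The expected number is an assumption (0 to 1 per arm), and a 4-point shift is small against intervals as wide as those at this sample size.

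For tumor change, and for ORR after a clinically based crossover, the fault is an omission: later scans are not excluded, although 6.7.4 points to their being handled separately. The effect on Arm 2 cannot be sized from the documents. The point is worth correcting because it removes an internal contradiction and a possible bias at little cost.

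**What to change.** 1. Define one window for 6.5.2.1, 6.5.4.1 and 6.5.4.3: from randomization to the earliest of objectively documented progression, start of subsequent anti-cancer therapy, or, in Arm 2, the first crossover dose. CR+PR in the best-response table then equals ORR. Aligning on objective progression rather than the wider definition is a choice, but it matches Protocol 10.2.1. Use the same term in both sentences of 6.5.2.1.
2. Use the same progression definition for the duration of response of those responders, as the protocol's definition in 10.2.2 does, with the censoring date to match.
3. Keep responses after pseudoprogression in ORR4 (6.5.2.2) and reconcile this with Protocol 10.2.1, which treats such a response as the true one. Complete the unfinished pseudoprogression sentence in 6.5.2.1 at the same time.
4. Show tumor change after the window in a labelled supplementary summary.

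Cost: SAP wording and programming, with no new data. The downside is that later scans, including shrinkage after pseudoprogression, leave the main tumor-change summary; item 4 keeps them visible.
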